## 7.2 Documentation of non-serious AEs or SARs

For non-serious AEs or SARs, documentation must begin from day 1 of study treatment and continue through the 30 day follow-up period after treatment is discontinued.

Collected information should be recorded in the Case Report Forms (CRF) for that patient. Please include a description of the event, its severity or toxicity grade, onset and resolved dates (if applicable), and the relationship to the study drug. Documentation should occur at least monthly.

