**B.** If whole body CT scan with IV contrast has been previously performed, time elapsed between the pre-study “diagnostic” CT scan with IV contrast and treatment initiation with pembrolizumab should be at most 28 days. In this case, a whole body PET scan must be performed within 28 days prior to C11-AMT PET imaging.

**C.** If both whole body PET scan and a CT scan with IV contrast (chest, abdomen, pelvis and neck if applicable) have been performed separately prior to study entry, this is acceptable as long as the whole body PET scan is within 28 days of C11-AMT PET imaging and the CT with IV contrast is within 28 days of starting pembrolizumab.

Following pembrolizumab infusions administered every 3 weeks x 4 cycles, antitumor response will be assessed at 12 weeks by performing a whole body FDG PET scan coregistered with CTIVC. As an alternative, CTIVC of the chest, abdomen, and pelvis (add neck, if applicable) is acceptable and can be used for this assessment of antitumor response by RECIST v1.1 criteria. It is quite possible that patients may progress earlier than 12 weeks; in this case, an evaluable patient will be a patient who has received at least two pembrolizumab infusions and subsequently had restaging scans to document radiographic progression and measurement by RECIST v1.1 criteria. Antitumor response will then be correlated with various C11-AMT PET parameters at baseline (e.g. SUVmax, total tumor metabolic volume, measurement of intra-tumoral and inter-lesion heterogeneity), which is the primary endpoint of the study. Toxicity will be assessed during treatment via NCI CTCAE v4.03. Following week 12, subjects will have completed study treatment requirements, and after discussion with their doctor they will be allowed to continue pembrolizumab per standard of care until disease progression or other reasons (e.g., unacceptable toxicity). Long-term follow up and treatment of all patients who continue to have clinical benefit from pembrolizumab (complete response, partial response, stable disease) will be maintained as per standard of care.

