#### 4.2.1 Treatment Dosage and Administration

After screening and pretreatment, treatment will consist of the following:

Pembrolizumab 200mg IV flat dose will be administered over 30 minutes on Day 1; Pembrolizumab dosing will be repeated every 3 weeks until progression or subject withdrawal for other reasons.

Agent	Dose/Frequency	Route	Schedule
Pembrolizumab	200mg every 3 weeks	IV over 30 minutes	Starting on D1 of study; Every 3 weeks (21 days) until disease progression or withdrawal for other reasons

On-study treatment is 12 weeks of pembrolizumab.

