#### 4.7 Duration of Follow Up

Subjects will be followed for up to 3 years after removal from study treatment or until death, whichever occurs first. Patients removed from study for unacceptable adverse events (AEs) will be followed until resolution or stabilization of the event(s).

The long-term follow-up visit is defined as 90 days ( $\pm 15$  days) after the last dose of treatment (see Section 6.1). All adverse events should be followed until this initial long-term follow-up visit (90 days after last pembrolizumab dose).

Subsequent follow-up visits, defined as every 90 days thereafter ( $\pm 15$  days) for up to 3 years or until death (whichever is first) may be conducted via telephone or

chart review. These visits will be limited to history of any subsequent cancer treatments, an assessment of any SAE's considered to be possibly or probably related to study treatment until resolution, and survival status.

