##### Immune-Mediated Pneumonitis

Pneumonitis occurred in  $\sim 3\%$  of melanoma patients treated in clinical trials of pembrolizumab. The median time to development of pneumonitis was 5 months with a median duration of 4.9 months. The one patient with Grade 3 pneumonitis required initial treatment with high-dose systemic corticosteroids (greater than or equal to 40 mg prednisone or equivalent per day) followed by a corticosteroid taper. Pneumonitis completely resolved in seven of the nine patients with Grade 2-3 pneumonitis.

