#### Immune-Mediated Hypothyroidism

Hypothyroidism occurred in 34 (8.3%) of 411 melanoma patients treated in clinical trials of pembrolizumab. The median time to onset of hypothyroidism was 3.5 months. All but two of the patients with hypothyroidism were treated with long-term thyroid hormone replacement therapy. The other two patients only required short-term thyroid hormone replacement therapy. No patient received corticosteroids or discontinued pembrolizumab for management of hypothyroidism. Thyroid disorders can occur at any time during treatment.

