#### 6.4 Long-term follow up (90 days after week 12 dose of pembroluzimab)

Clinical evaluation: focused history on symptoms/toxicity.

Toxicity: Per NCI CTCAEv4.03; Serious adverse events (SAEs; or follow-up to any SAEs) that occur within 90 days of the end of pembrolizumab (or prior to start of new anti-cancer therapy, whichever is earlier) or any grade of Events of Clinical Interest (see section 7.3) that occur within 90 days of the end of pembrolizumab or 30 days after the initiation of a new anti-cancer therapy (whichever is earlier) must be recorded.

Survival analysis:

**Note:** Subsequent follow-up visits to occur every 90 days ( $\pm$  15 days) for up to 3 years or until death (whichever is first) may be conducted via telephone or chart review, and will be limited to history, date of progression on or following pembrolizumab therapy, if any subsequent cancer treatments were given, an assessment of any SAE's considered to be possibly or probably related to study treatment until resolution, and survival status.

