## 7.0 ADVERSE EVENTS

### 7.1 Definitions

#### 7.1.1 Adverse Event (AE)

An adverse event (AE) is any untoward medical occurrence (e.g., an abnormal laboratory finding, symptom, or disease temporally associated with the use of a drug) in a patient or clinical investigation subject administered a pharmaceutical product and which does not necessarily have a causal relationship with this treatment. An AE can therefore be any unfavorable and unintended sign (including an abnormal laboratory finding), symptom, or disease temporally associated with the use of a medicinal product, whether or not related to the medicinal product.

Hospitalization for elective surgery or routine clinical procedures that are not the result of an AE (e.g., surgical insertion of central line) need not be considered AEs and should not be recorded as an AE. Disease progression should not be recorded as an AE, unless it is attributable by the investigator to the study therapy.

Adverse events may occur during the course of the use of Merck product in clinical trials, or as prescribed in clinical practice, from overdose (whether accidental or intentional), from abuse and from withdrawal.

Progression of the cancer under study is not considered an adverse event.

All adverse events that occur after the consent form is signed but before treatment allocation/randomization must be reported by the investigator if they cause the subject to be excluded from the trial, or are the result of a protocol-specified intervention, including but not limited to washout or discontinuation of usual therapy, diet, placebo treatment or a procedure.

From the time of treatment through 30 days following cessation of treatment, all adverse events must be reported by the investigator. Such events will be recorded at each examination on the Adverse Event case report forms/worksheets. The reporting timeframe for adverse events meeting any serious criteria is described in section 7.2.3.1. The investigator will make every attempt to follow all subjects with non-serious adverse events for outcome.

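### Non-serious adverse event recording closes 30 days after treatment stops, before the protocol's own median onset of pneumonitis and colitis, and section 4.7 leaves unclear whether new events are collected to 90 days

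*Combined protocol and SAP*

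**What the plan says.** Two sections set the end of general adverse event recording. Section 7.1.1: "From the time of treatment through 30 days following cessation of treatment, all adverse events must be reported by the investigator". Section 7.2, for non-serious events: "documentation must begin from day 1 of study treatment and continue through the 30 day follow-up period after treatment is discontinued".

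Section 4.7 describes follow-up differently: "All adverse events should be followed until this initial long-term follow-up visit (90 days after last pembrolizumab dose". The Time and Events Table marks a toxicity evaluation in the long-term follow-up column, and section 6.4 specifies "Clinical evaluation: focused history on symptoms/toxicity". Footnote 4 of the table and section 6.4 then name what must be recorded from that period: serious events and any-grade events of clinical interest. Section 7.3.1 also runs serious events to 90 days, or to new anti-cancer treatment if earlier.

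On timing of treatment, section 4.2 refers to the assessment "Following pembrolizumab infusions administered every 3 weeks x 4 cycles" and section 4.2.1 states "On-study treatment is 12 weeks of pembrolizumab". On timing of harms, section 5.1.6 says of hypothyroidism "The median time to onset of hypothyroidism was 3.5 months" and of pneumonitis "The median time to development of pneumonitis was 5 months"; it gives 6.5 months for colitis. Section 4.3.1.2 accepts that immune events can begin months after dosing has ended.

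**The concern.** The protocol expects some immune-mediated harms to appear late, yet its general recording window is short. A patient who reports a new non-serious event at the 90-day visit has been asked about toxicity, but no section clearly requires the answer to be entered. The listed events of clinical interest (section 7.3.3.1) are overdose and a combined liver-test criterion, so thyroid, lung and bowel events do not enter by that route.

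The anchor is also unclear. Sections 7.1.1 and 7.2 count from cessation or discontinuation of treatment. Footnote 4 counts the first long-term visit from the last on-study dose. The heading of section 6.4 refers to a week 12 dose, although the table shows no infusion after day 1 of cycle 4. Patients with clinical benefit may continue pembrolizumab as standard of care, so cessation can be read in more than one way. Sites could apply different windows, and events not entered at the time may not be recoverable. What is at stake is the completeness of the toxicity record.

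**Working it through.** The plan gives no figure to reproduce; the check is date arithmetic followed by a rough size.

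**Inputs.** Four infusions at 3-week intervals (4.2). On-study treatment of 12 weeks (4.2.1), which agrees with 4 × 21 = 84 days. Windows of 30 days (7.1.1, 7.2) and 90 days (4.7). Median onsets of 3.5, 5 and 6.5 months (5.1.6). One month = 30.4375 days.

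**Step 1: when each window closes.** The fourth dose falls 3 × 21 = 63 days after the first.

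| Anchor | +30 days | +90 days |
|---|---|---|
| Fourth dose (day 63 after first) | 93 days = 3.06 months | 153 days = 5.03 months |
| Week 12 (day 84 after first) | 114 days = 3.75 months | 174 days = 5.72 months |

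One 3-week interruption also gives 114 days.

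**Step 2: comparison with the medians.**

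| Event | Median | 30 days from fourth dose (3.06) | 30 days from week 12 (3.75) | 90 days from fourth dose (5.03) |
|---|---|---|---|---|
| Hypothyroidism | 3.5 | closes before | closes after | closes after |
| Pneumonitis | 5 | closes before | closes before | just reaches |
| Colitis | 6.5 | closes before | closes before | closes before |

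Not every immune event is late: the median for hyperthyroidism is 1.5 months, inside every window.

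**Step 3: rough size.** Assume exponential onset through each stated median, so that the share captured by time t is 1 − 0.5^(t/median). Incidences are 8.3% for hypothyroidism (5.1.6), and 2.7% for pneumonitis and 1.7% for colitis (1.3.2). Windows run from the fourth dose.

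| Event | Expected in 27 | Share by 3.06 months | Share by 5.03 months | Added events |
|---|---|---|---|---|
| Hypothyroidism | 27 × 0.083 = 2.24 | 0.45 | 0.63 | 2.24 × 0.176 = 0.40 |
| Pneumonitis | 27 × 0.027 = 0.73 | 0.35 | 0.50 | 0.73 × 0.157 = 0.11 |
| Colitis | 27 × 0.017 = 0.46 | 0.28 | 0.41 | 0.46 × 0.137 = 0.06 |

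The total is 0.40 + 0.11 + 0.06 = 0.57, or about 0.6 events. If the present 30 days are already counted from week 12 and the visit stays 90 days after the fourth dose, the gains in share are 0.107, 0.097 and 0.086. The total is then 0.24 + 0.07 + 0.04 = 0.35. These counts include serious events, which are already recorded to 90 days, so the gain in non-serious events is smaller still.

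**Step 4: grade.** From section 1.3.2, the share below grade 3 is (7.5 − 0.2)/7.5 = 97% for hypothyroidism, (2.7 − 0.3)/2.7 = 89% for pneumonitis and (1.7 − 1.1)/1.7 = 35% for colitis.

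**The case against.** The strongest reply is that the windows form a deliberate tier: general events to 30 days, serious events and events of clinical interest to 90, with concomitant medications also recorded to 30 days (4.4.1). On that view, *followed* in section 4.7 means tracking events already recorded, and a clarifying word there would be enough. This stands in part. A reader might infer a flat contradiction between 4.7 and 7.1.1/7.2, but the wording allows either meaning. What remains is an ambiguity, together with a visit that elicits toxicity and does not clearly require it to be entered.

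A reader might also infer that most late immune harms are low grade and therefore escape the serious-event window. The documents do not support this for colitis, where about two thirds of cases are grade 3-4. Nor is grade the same as seriousness: section 7.1.4 defines serious events by outcome and includes important medical events, so some grade 2 pneumonitis could qualify.

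The gain is also limited. Thyroid panels are scheduled at screening, cycle 3 and end of treatment, not at the 90-day visit, so a history there would miss asymptomatic thyroid change. Section 6.6 points to a separate guidance document on immune-related events, which might capture some cases, but the protocol's own list does not name these three. Finally, no objective or endpoint in section 2 concerns safety and section 8 specifies no toxicity analysis. That limits the consequence, although section 6.6 makes every treated patient evaluable for toxicity.

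**Conclusion.** The point holds as a modest truncation of the toxicity record and an unclear window. For pneumonitis and colitis, the 30-day cutoff precedes the stated median on both anchors tested. For hypothyroidism it does so only when counted from the fourth dose; from week 12 the comparison reverses (3.75 against 3.5 months). It would be wrong to conclude that all three harms would mostly go unrecorded whatever the reading.

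The size is about 0.35 to 0.6 events in 27 patients. It rests on an assumed exponential onset and on medians from earlier pembrolizumab trials whose treatment duration section 5.1.6 does not give. The date comparison does not need the exponential assumption. No primary or secondary endpoint changes. A 90-day window would still close before the colitis median. This is an inexpensive improvement worth making, and the trial's conclusions about the imaging biomarker do not depend on it.

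**What to change.** Reconcile section 4.7, the Time and Events Table with footnote 4, and sections 6.4, 7.1.1 and 7.2 into one window and one anchor for non-serious adverse events. The anchor should be the last on-study dose. Record on the adverse event form any non-serious event elicited at the existing long-term visit (90 ± 15 days after that dose). For patients who continue standard-of-care pembrolizumab, add a flag for onset after the on-study period.

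State with any toxicity summary that events after about 5 months are under-counted, as are asymptomatic thyroid changes not tested at that visit.

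The cost is a wording change and slightly more data entry for up to 27 patients. It needs no new visit or test and changes no treatment rule.

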### 7.3 SAEs or Serious SARs

#### 7.3.1 Timing

After informed consent but prior to initiation of study medications, only SAEs caused by a protocol-mandated intervention will be collected (e.g. SAEs related to invasive procedures such as biopsies, medication washout).

For any other experience or condition that meets the definition of an SAE or a serious SAR, recording of the event must begin from day 1 of study treatment and continue through the 90-day follow-up period after treatment is discontinued (or to the initiation of new anti-cancer treatment, whichever is earliest).

#### 7.3.2 Documentation and Notification

These events (SAEs or Serious SARs) must be recorded in the SAE console within Oncore™ for that patient within 24 hours of learning of its occurrence.

#### 7.3.3 Reporting

##### **IRB Reporting Requirements:**

##### UNC:

- The UNC-IRB will be notified of all SAEs that qualify as an Unanticipated Problem as per the UNC IRB Policies using the IRB's web-based reporting system (see section 9.5.3) within 7 days of the Investigator becoming aware of the problem.

Affiliate sites (Required wording if multicenter):

- For affiliate sites using a local IRB of record, please submit adverse events per local IRB policy.
- For affiliate sites relying on the UNC-IRB, an aggregated list of all SAEs will be submitted to the UNC IRB annually at the time of study renewal according to the UNC IRB policies and procedures. In addition, any SAEs that qualify as an Unanticipated Problem will be entered into Oncore and reported to the UNC IRB by the Multicenter Regulatory Associate using the IRB's web-based reporting system within 7 days of the Investigator becoming aware of the problem.

##### Pregnancy

Although pregnancy and lactation are not considered adverse events, it is the responsibility of investigators or their designees to report any pregnancy or lactation in a subject (spontaneously reported to them) that occurs during the trial.

Pregnancies and lactations that occur after the consent form is signed but before treatment allocation/randomization must be reported by the investigator if they cause the subject to be excluded from the trial or are the result of a protocol-specified intervention, including but not limited to washout or discontinuation of usual therapy, diet, placebo treatment or a procedure.

For Affiliate sites, the pregnancy, suspected pregnancy, or positive pregnancy test must be reported to the Multicenter Project Manager immediately (within 24 hours) via email (preferred) or facsimile to [contact]. The Multicenter Project Manager will then report the event to the Funding Source (see requirements below).

Pregnancies and lactations that occur from the time of treatment allocation/randomization through 120 days following cessation of Sponsor's product, or 30 days following cessation of treatment if the subject initiates new anticancer therapy, whichever is earlier, must be reported by the investigator. All reported pregnancies must be followed to the completion/termination of the pregnancy. Pregnancy outcomes of spontaneous abortion, missed abortion, benign hydatidiform mole, blighted ovum, fetal death, intrauterine death, miscarriage and stillbirth must be reported as serious events (Important Medical Events). If the pregnancy continues to term, the outcome (health of infant) must also be reported.

Such events must be reported within 24 hours to the Sponsor and within 2 working days to Merck Global Safety. (Attn: Worldwide Product Safety; [contact])

The Investigator will follow the female subject until completion of the pregnancy and must document the outcome of the pregnancy (either normal or abnormal outcome) and report the condition of the fetus or newborn to the Multicenter Project Manager. If the outcome of the pregnancy was abnormal (e.g., spontaneous or therapeutic abortion), the Investigator should report the abnormal outcome as an AE. If the abnormal outcome meets any of the serious criteria, it must be reported as an SAE.

**FDA Expedited Reporting requirements:**

A sponsor must report any suspected adverse reaction that is both serious and unexpected to the FDA. The sponsor must report an adverse event as a suspected adverse reaction only if there is evidence to suggest a causal relationship between the drug and the adverse event, such as:

- A single occurrence of an event that is uncommon and known to be strongly associated with drug exposure (e.g., angioedema, hepatic injury, Stevens-Johnson Syndrome);
- One or more occurrences of an event that is not commonly associated with drug exposure, but is otherwise uncommon in the population exposed to the drug (e.g. tendon rupture);
- An aggregate analysis of specific events observed in a clinical trial (such as known consequences of underlying disease or condition under investigation or other events that commonly occur in the study population independent of drug therapy) that indicates those events occur more frequently in the drug treatment group than in a concurrent or historical control group.

The sponsor must submit each IND safety report on FDA Form 3500A. Each notification to FDA must bear prominent identification of its contents, i.e., “IND Safety Report,” and must be transmitted to the review division that has the responsibility for review of the IND. In each IND safety report, the sponsor must identify all IND safety reports previously submitted to FDA concerning a similar suspected adverse reaction and must analyze the significance of the suspected adverse reaction in light of previous, similar reports or any other relevant information.

#### Timing

FDA must be notified of potential serious risks within 15 calendar days after the sponsor determines the event requires reporting. FDA must be notified of unexpected fatal or life-threatening suspected adverse reactions as soon as possible but in no case later than 7 calendar days after the sponsor’s initial receipt of the information. For Multicenter trials, Lineberger is the sponsor, therefore, the Multicenter Project Manager must be notified of the SAE within 24 hours of the event. If the results of a sponsor’s investigation show that an adverse event not initially determined to be reportable is reportable, the sponsor must report such suspected adverse reaction in an IND safety report as soon as possible, but in no case later than 15 calendar days after the determination is made.

#### Follow-up

The sponsor must promptly investigate all safety information it receives. Relevant follow-up information to an IND safety report must be submitted as soon as the information is available and must be identified as such, i.e., “Follow-up IND Safety Report.” Additionally, upon request from FDA, the sponsor must submit to FDA any additional data or information that the agency deems necessary, as soon as possible, but in no case later than 15 calendar days after receiving the request.

